8.2 Adverse Events

Adverse events will be collected from the date caregiver signs informed consent form up to the post-treatment safety follow-up visit. All AEs occurring during the trial, whether attributed to the IMP or not, observed by the investigator, or reported by the caregiver, will be recorded in the eCRF. AEs will be coded using the latest version of MedDRA at the time of reportig, associating lower-level terms with preferred terms and system organ classes by the primary hierarchy. Treatment-emergent AEs (TEAEs) are AEs that started, or worsened in severity or seriousness, following the first dose of IMP.

An AE profile for the Safety analysis set will be provided, which summarizes the subject incidence by treatment received, for the following information:

- Any TEAEs
- TEAEs related to treatment
- Serious TEAEs
- Serious TEAEs related to treatment
- TEAEs leading to withdrawal of IMP
- TEAEs related to treatment leading to withdrawal of IMP
- TEAE leading to death

AE summaries will include TEAEs. AE descriptions will be presented by decreasing frequency across all patients for a given SOC and Preferred Term. The tables will display counts and percentages of subjects who reported at least one AE in each system organ class represented in the AE data. Within each system organ class, the tables will display the counts and percentages of subjects reporting at least one AE, as designated by the preferred terms.

The following AE summaries will be produced:

- TEAEs by SOC and PT
- TEAEs related to treatment by SOC and PT. This table will include TEAEs that have a plausible relationship to the IMP as assessed by the investigator.
- TEAEs by SOC, PT, and maximum severity. On this table, treatment groups will be subdivided into three potential grades of AE severity— Mild, Moderate, Severe. TEAEs missing a severity grade will be imputed as 'Severe'.
- TEAEs by SOC, PT, and sex
- TEAEs by SOC, PT, and time of first onset (<1 week, 1-<4 weeks, 4-<12 weeks, >=12 weeks)
- TEAEs by SOC, PT, and time to AE resolution (<1 week, 1 week, 2 weeks, 3 weeks, 4 weeks, >=5 weeks, ongoing).
- Serious TEAEs by SOC and PT
- Serious TEAEs related to treatment by SOC and PT. The same approach applies as described for TEAEs related to treatment.
- TEAEs leading to study withdrawal by SOC and PT. This subset includes "Study Discontinuation" due to TEAEs.
- TEAEs leading to withdrawal of IMP by SOC and PT. This subset includes TEAEs with an Action Taken of "Drug Withdrawn." Withdrawal means permanent discontinuation of IMP.
- Treatment related TEAEs leading to withdrawal of IMP by SOC and PT. This subset includes TEAEs with an Action Taken of "Drug Withdrawn." Withdrawal means permanent discontinuation of IMP.
- TEAEs leading to dose reductions by SOC and PT. This subset includes TEAEs with an Action Taken of "Dose Reduced."
- TEAEs related to treatment leading to dose reductions by SOC and PT. This subset includes TEAEs with an Action Taken of "Dose Reduced."
- TEAEs leading to dose reductions and are resolved by SOC and PT. This subset includes TEAEs with an Action Taken of "Dose Reduced" and Outcome "Recovered/Resolved" or "Recovered/Resolved with Sequelae".
- TEAEs leading to dose interruptions by SOC and PT. This subset includes TEAEs with an Action Taken of "Dose Interrupted."
- TEAEs related to treatment leading to dose interruptions by SOC and PT. This subset includes TEAEs with an Action Taken of "Dose Interrupted."
- TEAEs leading to dose interruptions and are resolved by SOC and PT. This subset includes TEAEs with an Action Taken of "Dose Interrupted" and Outcome "Recovered/Resolved" or "Recovered/Resolved with Sequelae".
- Fatal TEAEs by SOC and PT. This subset includes TEAEs with Outcome "Fatal".

 Treatment-emergent AESIs by SOC and PT. The definition of AESI is described in Section 8.1.3.

The following AE listings will be prepared:

- All AEs
- Serious TEAEs
- TEAEs related to treatment
- TEAEs leading to drug withdrawal
- Fatal TEAEs
- Treatment-emergent AESIs

8.2.1 Adverse Events of Special Interest

Treatment-emergent AESIs will be summarized as described in Section 8.1.2.

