In general, the key risks identified from the clinical development program for LGS and DS are broadly expected to be the same for the ASD population – as the patient demographics and comorbidities have a significant amount of overlap. It is important to note that several of the key

risks for CBD-OS are dose related, as such the lower doses planned for the current trial may improve the tolerability of CBD-OS:

Hepatocellular injury is anticipated to be an important risk for CBD-OS in ASD patients, although to date the transaminase elevations observed with CBD-OS treatment have generally been asymptomatic, with no Hy's law cases reported from any source. The proposed dose level of 10 mg/kg/day may provide an improved tolerability compared to the 10 and 20 mg/kg/day doses employed in the LGS and DS program. Furthermore, the transaminase elevations in LGS and DS patients were markedly more frequent and of a greater magnitude in patients taking concomitant VPA. Of note, VPA use is expected to be less frequent in the ASD population than in the LGS and DS populations, providing an additional avenue to an improved tolerability to CBD-OS with respect to potential hepatocellular injury.

Somnolence type events are anticipated to be important risks for CBD-OS in ASD patients; however, from experience in LGS and DS patients, such events were manageable, and only a minority needed to discontinue CBD-OS. Dose adjustment should help mitigate any events of somnolence and sedation if needed. The somnolence may also diminish with repeated dosing over time.

Cannabidiol oral solution has been shown to cause loss of weight in clinical trials, however the incidence of a significant loss of weight (> 5%) was noted to be similar between the CBD-OS dose of 10 mg/kg/day and placebo in placebo-controlled trials. There was no impact on growth, as measured through BMI or height in these trials.

In DS/LGS studies, aggression was reported in 2.2% of patients in the 10 mg/kg/day group while irritability was reported in 7.2% of patients in the 10 mg/kg/day group. The majority of cases reported were of mild or moderate severity with only few cases leading to withdrawal from these trials.

A higher incidence of pneumonia was noted with CBD-OS in LGS and DS controlled trials, although incidence does not appear to be dose related, majority of patients has risk factors for pneumonia and no plausible mechanism has been identified.

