3.3.2 Choice of Dosing Regimen

Doses of up to 50 mg/kg/day GWP42003-P have been administered in the GW clinical development programs for GWP42003-P. At the time of protocol authoring, a total of approximately 4,973 subjects have received GWP42003-P from blinded and open-label GW-sponsored trials and supportive programs (expanded access and other compassionate use programs), including patients with epilepsy (data cutoff date: Feb 2020). From these data sources the following warnings and precautions were established: hepatocellular injury, somnolence and sedation, suicidal behavior and ideation, hypersensitivity reactions, and withdrawal of AEDs. Of note, routine liver monitoring is required with the use of CBD-OS. To date, the available safety data collected showed that the reported AEs were usually mild or moderate in severity and resolved. There have been few withdrawals due to AEs.

Efficacy of CBD against cognitive and social behavioral deficits in relevant animal models has been found over a range of doses from 2 to 200 mg/kg in a model and endpoint dependent manner⁶, with the top dose of the tested dose range overlapping with the effective anticonvulsive dose range of 50 to 200 mg/kg/day in nonclinical models⁶. It is therefore expected that clinical anticonvulsant doses (10 mg/kg/day and 20 mg/kg/day as per studies in LGS or DS patients) should provide meaningful exposures to explore efficacy in ASD.

The doses used across the investigations reported in the literature referencing the use of CBD and THC in ASD are variable but mostly fall between 2 and 10 mg/kg/day CBD. In particular, the target dose in the randomized, placebo-controlled trial⁹ was 10 mg/kg day CBD (with a maximum CBD daily dose of 420 mg and an average daily dose of 5.5 mg/kg/day).

The GWND19189 trial will evaluate the efficacy and safety of 10 mg/kg/day CBD-OS (dosed as 5 mg/kg/day b.i.d.) versus placebo. The dose of 10 mg/kg day was selected as it is within the

clinical therapeutic range for GWP42003-P in pediatric epileptic encephalopathies (LGS and DS).

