9.1.13 Adverse Events

Any adverse changes in the patient's medical condition, following completion of the consent form by the caregiver, will be recorded on the eCRF as AEs, after questioning the caregiver further if necessary. All AEs occurring during the trial, whether attributed to the IMP or not, observed by the investigator, or reported by the caregiver, will be recorded in the eCRF.

Any AE which meets SAE criteria should be reported as a SAE.

SAEs must be reported to GW PVD within 24 hours of discovery or notification of the event via recording in the eCRF.

Adverse events inferring to hepatic enzymes increased, rash, pneumonia, cognitive disorders and self-injurious ideation or intentional self-injury may be considered as AESI by GW PVD and additional information may be requested during follow-up.

Refer to Section 12 for definitions, procedures and further information on AE reporting.

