12.7 Follow-up Procedures for Adverse Events

The investigator may be asked to provide follow-up information to the GW PVD for any AEs reported or during the investigation of potential safety issues. Such requests for additional safety information may occur after a patient has finished a trial.

Additional information may also be requested by GW PVD if a patient experiences any adverse events that is considered an AESI, these include any events that may infer to hepatic enzymes increased, rash, pneumonia, cognitive disorders and self-injurious ideation or intentional self-injury.

AEs considered related to the IMP by the investigator or the sponsor should be followed up until resolution or the event is considered stable.

It will be left to the investigator's clinical judgment whether an AE is of sufficient severity to require the patient's removal from treatment. A patient may also voluntarily withdraw from treatment due to what he or she perceives as an intolerable AE. Further details of withdrawal are presented in Section 10. If either of these occurs, the patient must undergo an end of treatment assessment and be given appropriate care under medical supervision until symptoms cease or the condition becomes stable. If a safety concern is identified following withdrawal of a patient, GW may contact the investigator for additional follow-up information.

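### The protocol treats somnolence and sedation as one important expected risk, but no planned table counts the patients in each arm with at least one such event.

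*SAP*

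**What the plan says.** **How the protocol describes the risk.** Protocol 3.2 states: "Somnolence type events are anticipated to be important risks for CBD-OS in ASD patients". Later in the same paragraph it speaks of somnolence and sedation together. Protocol 3.3.2 gives the established warnings and precautions as "hepatocellular injury, somnolence and sedation, suicidal behavior and ideation, hypersensitivity reactions, and withdrawal of AEDs", so the two terms form one item there as well.

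**What counts as an AESI.** Protocol 9.1.13 reads: "Adverse events inferring to hepatic enzymes increased, rash, pneumonia, cognitive disorders and self-injurious ideation or intentional self-injury may be considered as AESI". Protocol 12.7 repeats these topics. Neither place names somnolence or sedation.

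**What the SAP does with AESIs.** SAP 8.2 plans a treatment-emergent AESI table by system organ class (SOC) and preferred term (PT), and adds: "The definition of AESI is described in Section 8.1.3". SAP 8.2.1 consists of one sentence: "Treatment-emergent AESIs will be summarized as described in Section 8.1.2". SAP 8.1 covers exposure and treatment compliance and has no numbered subsections, so both references lead nowhere. The SAP itself lists no AESI terms.

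**How adverse events are tabulated.** SAP 8.2 gives an overall profile (any event, related, serious, leading to withdrawal, fatal). Every table that separates kinds of event is then by SOC and PT: overall, and by relatedness, severity, sex, onset, resolution, seriousness and action taken. Protocol 13.6.3.2 also plans descriptive tables by PT and SOC.

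**The concern.** The protocol's own unit of risk is the class of somnolence-type events. The planned tables use a different unit, the single preferred term. A reader who asks how many children in each arm had any somnolence or sedation event will find no row with the answer.

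Protocol 3.2 applies the description of an important anticipated risk in these patients to two harms: hepatocellular injury and somnolence-type events. The first has a dedicated table of threshold criteria in SAP 8.3. The second has no dedicated summary.

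What is at stake is estimation: one incidence per arm for a known harm of the drug, and the difference between arms with its uncertainty. Protocol 3.2 also suggests that somnolence may lessen as dosing continues. The SAP's onset and resolution windows bear on that, but as planned they describe it one term at a time.

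**Working it through.** **1. Is there any planned count for the class?**

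| Planned output | Does it count patients with any somnolence or sedation event? |
|---|---|
| Overall profile (SAP 8.2) | No. It covers all events together. |
| SOC rows (SAP 8.2) | No. A SOC row takes in every event in that organ class, related to sedation or not. |
| PT rows (SAP 8.2) | No. There is one row per term, and a patient with two terms appears in both. |
| AESI table (SAP 8.2, 8.2.1) | No. The class is not among the protocol's topics, and the table is by SOC and PT anyway. |
| Listing of all adverse events (SAP 8.2) | Not as a count. The count could be built from it once terms are chosen. |

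**2. Can the PT rows be combined?** Only within limits. For PT rates p1, p2, p3 in one arm:

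- lower limit (every patient with a rarer term also has the commonest one) = max(p1, p2, p3)
- upper limit (no patient has two terms) = p1 + p2 + p3

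**3. Inputs.** Protocol 13.1 randomizes 160 patients 1:1, so 160 / 2 = 80 per arm. The documents give no somnolence or sedation rate, so there is no plan figure to reproduce. The PT rates and the use of three terms are assumptions.

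| Assumed PT rates, active arm | Lower limit | Upper limit | Patients out of 80 |
|---|---|---|---|
| 6%, 4%, 3% | 6% | 6 + 4 + 3 = 13% | 4.8 to 10.4 |
| 10%, 5%, 4% | 10% | 10 + 5 + 4 = 19% | 8.0 to 15.2 |
| 15%, 5%, 5% | 15% | 15 + 5 + 5 = 25% | 12.0 to 20.0 |

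In the middle row, if the terms occurred independently, the combined rate would be 1 − 0.90 × 0.95 × 0.96 = 17.9%. Across the rows, the upper limit is 13/6 = 2.2, 19/10 = 1.9 and 25/15 = 1.7 times the largest single row.

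**4. Effect on the difference between arms.** Take the middle row and assume placebo rates of one quarter: 2.5%, 1.25% and 1%. The placebo limits are 2.5% and 2.5 + 1.25 + 1 = 4.75%. If overlap may differ between arms, the PT rows alone allow a risk difference from 10 − 4.75 = 5.25 points to 19 − 2.5 = 16.5 points.

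**5. What a grouped row would give.** At 20% versus 5%, the 95% CI half-width is 1.96 × √(0.20 × 0.80 / 80 + 0.05 × 0.95 / 80) = 10.0 points. That is not precise, but it is a direct estimate with a stated uncertainty.

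**The case against.** - **Table specifications are in a separate document (SAP 1 and 6), and a listing of all adverse events is planned.** This stands. A reader might infer that the combined incidence will never be estimated. The documents show only that it is not planned in the text available. What remains is that nothing there fixes the terms before unblinding.
- **The AESI list serves pharmacovigilance follow-up.** This also stands. Protocol 9.1.13 and 12.7 use it to request more information, and the wording is permissive. Absence from the list is not itself an analysis error, and adding the class would not be enough while AESIs are tabulated by PT. One might try to place sedation under cognitive disorders, but nothing assigns it there.
- **A reader might infer that separate rows would hide a real excess.** The documents do not support that. Protocol 13.6.3.2 makes adverse event reporting descriptive, and no test is specified. A reader also sees all the rows. With 80 per arm and three terms assumed at 8% versus 2%, at least one row reaches two-sided Fisher p<0.05 about 59% of the time if the terms are independent and 61% if no patient has two. A pooled row reaches it about 82% and 88% of the time. Splitting weakens the signal but does not bury it. With full overlap, pooling adds nothing.
- **A reader might extend the point to aggression and irritability.** Protocol 3.2 gives 2.2% and 7.2% at 10 mg/kg/day in the epilepsy studies, but does not call them important risks and gives no placebo rates. The ABC-I already compares irritability between arms.
- **A reader might infer that sedation would explain an ABC-I benefit.** The documents do not say so, and an incidence row per arm could not show it.

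**Conclusion.** The gap is real and limited. The protocol treats somnolence and sedation as one important risk, but the planned tables give no patient-level count for it, and the PT rows do not determine one. The illustrated range is 10% to 19% for rows of 10%, 5% and 4%. It rests on assumed rates, three assumed terms and 80 patients per arm, and it narrows to nothing if the same patients report every term.

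The two dead references are a separate editorial fault. The AESI topics can be recovered from Protocol 9.1.13 and 12.7, but the SAP alone does not define the table it plans.

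This concerns safety reporting only. It is a cheap improvement to make before unblinding and does not threaten the trial's validity.

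**What to change.** In SAP 8.2 and 8.2.1:

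1. Replace the references to Sections 8.1.2 and 8.1.3 with the protocol's AESI topics.
2. Add a somnolence/sedation group. Define it, and each AESI topic, by a preferred-term list fixed before unblinding.
3. Add one table of patients with at least one treatment-emergent event in each group, by arm, with the risk difference and 95% CI, the maximum severity, and the onset and resolution windows that SAP 8.2 already uses.

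**Cost.** A SAP wording change, one blinded review of terms and one extra table on data already collected. Deciding which terms belong to the group takes some judgment, and fixing the list while blinded controls that. No dose, clinical rule, efficacy analysis or sample size changes.

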8.3 Clinical Laboratory Results

Laboratory tests will include hematology, serum biochemistry, coagulation (Visit 1 only; thereafter only as an unscheduled assessment if ALT or AST > 3 x ULN), Clinical laboratory sample parameters are detailed in Table 9.1-1 in the study protocol. Urinary data and the drug abuse data will only be listed.

In case of values <LLoQ or >ULoQ, LLoQ or ULoQ, respectively, will be used in summary tables.

All test results and abnormal laboratory values will be presented in data listings.

Summaries of actual values and changes from baseline for numeric test results will be presented for each assessment time point.

Shift tables will be summarizing the counts and percentages of subject's baseline CTCAE grade versus worst CTCAE grade at any postbaseline visit.

Potential Cases of Drug-Induced Liver Injury

A table will summarize the number of subjects by the following criteria.

At baseline:

- ALT > 1 x ULN
- AST > 1 x ULN
- ALT or AST > 1 x ULN
- TBIL > 1 x ULN
- ALT or AST or TBIL > 1 x ULN

At any time point after first dose of study treatment:

- ALT > N x ULN, where N=1, 2, 3, 5, 8
- AST > N x ULN, where N=1, 2, 3, 5, 8
- ALT or AST > N x ULN, where N=1, 2, 3, 5, 8
- ALP > 2 x ULN
- TBIL > 1 x ULN
- TBIL > 2 x ULN
- ALT or AST > 3 x ULN and TBIL > 2 x ULN
- ALT or AST>3 x ULN and INR > 1.5

The summary table will be done by sex,

and

overall.

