9.1.9 Clinical Laboratory Sampling

The investigator should use their judgment and knowledge of the patient to determine when best to collect the blood and urine samples in order to mitigate the risk that invasive procedures may cause the patient to become stressed, thereby affecting the results of other assessments.

Laboratory tests will include hematology, biochemistry, coagulation (Visit 1 only; thereafter only as an unscheduled assessment if ALT or $AST > 3 \times ULN$) and urinalysis (provided urine can be obtained). Blood sample volume requirements and processing procedures will be detailed in a separate laboratory manual.

Urine samples for biochemistry will be analyzed at the trial site (or by the home nurse) by use of a dipstick with any relevant findings being sent for further urinalysis at the central laboratory (urinalysis, microscopy, culture, and sensitivity, as applicable). In cases where urine samples cannot be analyzed at the site (or by the home nurse) due to local regulations, a full set of urine samples should be sent to the central laboratory for analysis. Urine sample volume requirements and processing procedures will be detailed in a separate laboratory manual.

Urine samples for drugs of abuse will be sent to the central laboratory.

The investigator and trial monitor will be provided with a list of the normal ranges used by the testing laboratory for all variables assayed during the trial and a statement of accreditation (or similar) for the laboratory. Clinical laboratory sample parameters are detailed in Table 9.1-1.

Table 9.1-1Biochemistry, Hematology, Urinalysis, and THC					
Biochemistry (Serum) ^a	Hematology (Whole Blood) ^a	Coagulation (plasma) ^{a,b}	Urinalysis (Urine) ^c	Pregnancy Test (Serum) ^a	Drugs of Abuse (Urine) ^a
Alanine aminotransferase (ALT)	Hematocrit	Prothrombin time (PT/INR)	Bilirubin	Serum	Amphetamines
Albumin	Hemoglobin		Blood		Barbiturates
Alkaline phosphatase	Mean cell volume		Glucose		Benzodiazepine
Aspartate aminotransferase (AST)	Mean corpuscular hemoglobin		Ketones		Cannabinoids
Calcium	Platelets		Protein		Cocaine
Creatinine	Red blood cell count		Nitrites		Methadone
Creatinine clearance	White blood cell count with automated differential		рН		Opiates
Creatine kinase (CK)			Specific gravity		MDMA
Gamma-glutamyl transferase			Urobilinogen		Methamphetamines
Glucose			White blood cells		Oxycodone
HDL-cholesterol					Phencyclidine
Potassium					Tricyclic antidepressants
Prolactin					
Sodium					

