13.6.3.3 Clinical Laboratory Data

Clinical laboratory data will be summarized at screening, baseline, and at each time point during the treatment period using appropriate summary statistics. Categorical shift tables will be presented, showing the numbers of patients with values outside the normal range. Change from baseline will also be summarized by visit.

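### The protocol plans laboratory shift tables on the normal range; the SAP specifies only CTCAE-grade shifts, so out-of-range values without a grade have no committed count by arm

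*SAP*

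**What the plan says.** Clinical laboratory parameters are a named safety endpoint in both documents, to be compared between GWP42003-P and placebo (protocol 13.6.3; SAP Table 1 and Section 8).

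- **Protocol 13.6.3.3:** "Categorical shift tables will be presented, showing the numbers of patients with values outside the normal range". The sentence is not limited to particular analytes or to one direction.
- **SAP 8.3, scope:** "Clinical laboratory sample parameters are detailed in Table 9.1-1 in the study protocol".
- **SAP 8.3, shift tables:** "Shift tables will be summarizing the counts and percentages of subject's baseline CTCAE grade versus worst CTCAE grade at any postbaseline visit". No low/normal/high table is specified.
- **SAP 8.3, other laboratory displays:** "Summaries of actual values and changes from baseline for numeric test results will be presented for each assessment time point"; "All test results and abnormal laboratory values will be presented in data listings"; and a liver table with criteria such as "ALT or AST or TBIL > 1 x ULN".
- **SAP 8.3, urine:** "Urinary data and the drug abuse data will only be listed".
- **SAP 4.4:** unscheduled measurements are kept out of by-visit summaries. They are used only for a missing baseline or for worst-case displays such as shift tables.
- **Protocol 9.1.9:** the investigator and trial monitor receive "a list of the normal ranges used by the testing laboratory for all variables assayed during the trial".

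**The concern.** A toxicity grade and a low/normal/high category are different measures. The second exists for any analyte with a reference range, in both directions. The first exists only where the grading scale has a rule, and the SAP does not say which scale version or which rules apply. Replacing one with the other therefore removes the planned count for any value that is out of range but has no grade.

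What is at stake is a between-arm count in a pediatric safety comparison. Listings do not compare arms. Descriptive statistics show the centre, the spread and one extreme at each end, but not how many children moved out of range. Scheduled safety laboratory draws are also few. After screening, Appendix 1 has them at Visit 5 and Visit 9, or at Visit 8 for patients who do not taper. Unscheduled draws may therefore carry some of the relevant values, and those enter only worst-case displays.

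**Working it through.** No sample size, power or event figure is involved. The check compares the two texts and then looks for any other SAP display that would supply the missing count.

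**Step 1. Is the planned table in the SAP?** No. SAP 8.3 has one shift table, on CTCAE grade. The other SAP sections contain no normal-range laboratory table.

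**Step 2. How many analytes are in scope?** Protocol Table 9.1-1 lists 18 biochemistry analytes and 7 hematology analytes, counting white cells with differential as one: 18 + 7 = 25. PT/INR is separate. It is tested at Visit 1 and afterwards only if ALT or AST exceeds 3 × ULN.

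**Step 3. What does each other SAP display count?**

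| SAP display | Counts out-of-range patients? |
|---|---|
| Liver table (8.3) | Yes, upper direction only: ALT, AST and TBIL from 1 × ULN; ALP only above 2 × ULN; INR only jointly with ALT or AST above 3 × ULN |
| Descriptive summaries (Section 6, 8.3) | No: n, mean, SD, minimum, median, maximum by time point |
| Listings (8.3) | No: values by patient |
| TEAE tables (8.2) | Only results the investigator judged to be an AE (protocol 9.1.9) |

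**Step 4. What is left?** The liver table covers 4 of the 25 analytes (ALT, AST, TBIL, ALP). The other 25 − 4 = 21 depend wholly on the CTCAE shift for a laboratory count by arm. For the 4, low values, and ALP between 1 and 2 × ULN, depend on it too.

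**Step 5. What happens to an out-of-range value without a grade?**

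- *At a scheduled visit:* it contributes to the descriptive statistics and appears in a listing.
- *At an unscheduled draw after baseline:* SAP 4.4 excludes it from by-visit summaries, and the shift table has no cell for its abnormality. Outside the liver table's criteria, it appears only in listings.
- *In either case:* it is counted by arm if reported as a treatment-emergent AE, which depends on investigator judgment.

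**Step 6. How many values are affected?** This cannot be computed. If the chosen scale graded every analyte in both directions from the limit of normal, nothing would be lost. At the other extreme, all 21 analytes would have no count. The SAP supplies nothing that narrows this range.

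**The case against.** The strongest reply is that protocol Section 13 leaves analytical detail to the SAP, that a CTCAE shift is a recognised safety display, and that the main risk is well covered. Much of this stands. Hepatocellular injury is an anticipated risk the protocol stresses, and the liver table counts ALT, AST and bilirubin above 1 × ULN both at baseline and after dosing. Protocol 13.6.3.3 describes a display, not an endpoint definition, and prescribes no layout. The table shells are a separate document and could contain a normal-range table, although the SAP does not commit to one.

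Several stronger readings are tempting, and the documents do not support them:

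- *Out-of-range values would never be counted by arm.* Graded values, high ALT, AST and bilirubin, and results reported as AEs are all counted.
- *Only means are reported.* SAP Section 6 also gives SD, median, minimum and maximum.
- *Particular analytes, or a stated percentage of the panel, have no grade.* With no CTCAE version or grading table given, this would rest on an outside source.
- *The SAP merges low and high grades of one analyte.* It is silent on direction, and silence is not a decision to merge.
- *Prolactin is a special loss because antipsychotic use is common.* Antipsychotic use is a stratification factor, but no frequency is given, and whether prolactin is graded is not stated.
- *The change was left undisclosed.* The SAP's table of changes from the protocol is broken in the available text, so what it omits proves nothing.

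What the reply does not answer is that the protocol plans a normal-range count and no laboratory tabulation in the SAP supplies it beyond the liver criteria.

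**Conclusion.** The discrepancy holds, as a minor point. SAP 8.3 replaces a normal-range shift with a CTCAE-grade shift whose version, analytes and direction are unspecified. For 21 of 25 serum and hematology analytes, no other laboratory tabulation counts patients outside the range by arm. The loss is conditional: it applies to values that are out of range but ungraded, and its extent lies between nothing and all 21 analytes. No efficacy analysis is affected.

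The conclusion assumes that the SAP text governs the output and that the separate shells add no normal-range table.

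**What to change.** In SAP 8.3:

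1. Restore the normal-range shift, by treatment received, for every numeric serum and hematology analyte in protocol Table 9.1-1, using the central-laboratory ranges. One workable layout, which the protocol does not itself prescribe, is baseline low/normal/high against worst post-baseline low and, separately, worst post-baseline high. Unscheduled values should contribute, as SAP 4.4 already allows for worst-case displays. SAP 8.4 already separates high from low flags for vital signs and can serve as a model.
2. Keep the CTCAE shift as an addition, and state its version, the analytes graded and how direction is handled.
3. While editing, reconcile the listing-only rule for urine data with protocol 13.6.3.3, which makes no exception for urinalysis.

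If the sponsor prefers CTCAE shifts alone, the change should be recorded and justified in the section on changes from the protocol.

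The cost is a few sentences and routine table programming. The laboratory already supplies the ranges, and the liver table already needs upper limits. The downside is more pages of output.
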